5.2. Exclusion Criteria

Subjects will not be eligible for study participation if they meet any of the following criteria:

1. Any neurological condition that may place the subject at increased risk with exposure to botulinum toxin type A, including peripheral motor neuropathic diseases, such as amyotrophic lateral sclerosis and motor neuropathy, and neuromuscular junctional disorders, such as Lambert-Eaton syndrome and myasthenia gravis
2. Any history of facial nerve palsy (e.g., Bell's Palsy) or muscle weakness or paralysis in the treatment areas
3. Active skin disease, infections, or inflammation at the injection sites

[REDACTED]

5.3. Informed Consent and Authorization to Release Health Information

Written informed consent will be obtained from all subjects before any study-related procedures (including any screening procedures) are performed. The investigator may discuss the study and the possibility for entry with a potential subject without first obtaining consent. However, a subject wishing to participate must give written informed consent prior to any study-related procedures being conducted, including those performed solely for the purpose of determining eligibility for study participation, including withdrawal from current medication (if required prior to study entry). The investigator has both the ethical and legal responsibility to ensure that each subject being considered for inclusion in this study has been given a full explanation of the

procedures and expectations for study participation, as well as ample time to decide whether or not to participate and have all questions answered satisfactorily.

Each subject will sign the consent form that has been approved by the same IRB/IEC that was responsible for protocol approval. Each informed consent document must adhere to the ethical principles stated in the Declaration of Helsinki and will include the elements required by FDA regulations in 21 CFR Part 50, as well as the elements required by ICH GCP guideline, and applicable federal and local regulatory requirements. The consent form must also include a statement that Revance, their designees, auditing and regulatory agencies will have direct access to the subject's records and medical history for study related purposes.

Once the appropriate essential information has been provided to the subject and fully explained by the investigator (or a qualified designee) and it is felt that the subject understands the implications and risks of participating in the study, the IRB/IEC approved consent document shall be signed and dated by both the subject and the person obtaining consent (investigator or designee), and by any other parties required by the IRB/IEC or other regulatory authorities. The subject will be given a copy of the signed informed consent document with the original kept on file by the Investigator. All of the above activities must be completed before any study related procedures are conducted (including any screening study procedures).

5.4. Lifestyle Considerations

While enrolled in this study, subjects must agree to refrain from receiving non-ablative laser or light treatments, microdermabrasion, or chemical peels (medium depth or deeper, for example TCA or phenol) in the treatment areas within 3 months before enrollment through the end of the study.

██
██
Refer to Section 6.4 for a complete list of prohibited medications during the study.

5.5. Protocol Deviations

This study will be conducted as described in this protocol, except for emergency situations in which the protection, safety, and well-being of the subject requires immediate intervention, based on the judgment of the investigator (or a responsible, appropriately trained professional). In the event of a significant deviation from the protocol due to an emergency, accident, or mistake, the investigator or designee must contact Revance or designee by telephone at the earliest possible time. This will allow an early joint decision regarding the subject's continuation in the study. This decision will be documented by the investigator and Revance or designee.

5.6. Pregnancy

All WOCBP must use an effective method of birth control during the course of the study (e.g., oral contraceptive pill, injection, implant, patch, vaginal ring, intrauterine coil, intrauterine device, tubal ligation, barrier method) used WITH an additional form of contraception (e.g., sponge, spermicide or condom); abstinence; no heterosexual intercourse; or has a vasectomized

partner. A female is considered to be of childbearing potential UNLESS she is post-menopausal (no menses for 12 consecutive months) or without a uterus and/or both ovaries.

Before enrolling WOCBP in this study, investigators must review guidelines with the subject about study participation for WOCBP with the subject. The topics should generally include:

- Informed consent document
- Pregnancy prevention information
- Risks to unborn child(ren)
- Any drug interactions with hormonal contraceptives
- Contraceptives in current use
- Guidelines for the follow-up of a reported pregnancy

Prior to study enrollment, WOCBP must be advised of the importance of avoiding pregnancy during participation in this study and the potential risk factors for an unintentional pregnancy. The subject must sign the informed consent document stating that the risk factors for unintentional pregnancy and the consequences were discussed with her.

During the study, all WOCBP should be instructed to contact the investigator immediately (within 24 hours) if pregnancy is suspected (e.g., missed or late menstrual cycle). The investigator, or qualified designee, must immediately notify Revance or designee of any female subject who becomes pregnant any time during study participation, record the information on Revance or designee Pregnancy Notification Form and send the form to Revance or designee. The investigator will be asked to follow-up with the subject periodically during the pregnancy for ongoing health and safety information through term, as applicable.

If an SAE occurs in conjunction with the pregnancy such as untoward outcome of the pregnancy or of the offspring (spontaneous abortion, or abnormality in the offspring) then the reporting time frame for an SAE must be met and SAE reporting procedures followed. In the event of a normal birth, follow-up with the subject will occur with a phone call until the first well visit, at which time, active follow-up to the pregnancy will cease.

[REDACTED]

6.2.4. Investigational Product Administration

Investigational product will be administered by the PI to injection site in the designated treatment areas bilaterally while the subject is in a sitting position [REDACTED].

1. Wear protective gloves for investigational product administration
2. Pull subject's hair away from the treatment areas (lateral canthal region)
3. Wipe all injection sites with alcohol

[REDACTED]

[REDACTED]

[REDACTED]

[REDACTED]

[REDACTED]

- [REDACTED]
- [REDACTED]
- [REDACTED]
- [REDACTED]
- [REDACTED]
- [REDACTED]
- [REDACTED]
- [REDACTED]
- [REDACTED]
- [REDACTED]

6.3. Concomitant Medications/Therapies

[figure not shown]
Concomitant medications are any prescription or over-the-counter preparations used by subjects during participation in the study. Use of concomitant medications will be recorded on the Concomitant Medications electronic case report form (eCRF) beginning at the Screening Visit (and anything taken during the previous 30 days) until the Final Evaluation Visit.

[figure not shown]
The dose and dosing regimen of all prescription and non-prescription therapies and medications, including herbs, vitamins, or other nutritional supplements administered will be documented.

[REDACTED]

[REDACTED]

[REDACTED]

6.5. Dose Modification

Subjects will receive a single dose (consisting of 3 variable volume injections) according to assigned dose cohort in this study. The DRC will convene to review available data (including safety and photographs/videos) for Cohorts 1 and 2 prior to making a decision about the treatment of Cohort 3. The DRC will also convene to review applicable data (safety and photographs/video) prior to making a decision about the treatment of Cohort 4.

7. DISCONTINUATION OF STUDY INTERVENTION AND SUBJECT DISCONTINUATION/WITHDRAWAL

7.1. Subject Discontinuation/Withdrawal from the Study

A subject may voluntarily withdraw from study participation at any time. If the subject withdraws consent and discontinues from the study, the Investigator will attempt to determine the reason for discontinuation and record the reason in the subject's study records and on the eCRF. If a subject withdraws consent because of an AE, that AE should be indicated as the reason for withdrawal. In the event of early discontinuation, (i.e., prior to the Final Evaluation) and consent is withdrawn, the subject should be asked to return to the study center to complete the assessments specified in the Final Evaluation Visit. Subjects who withdraw from the study will not be replaced. Subjects who withdraw from the study, but agree to continued follow-up, must be re-consented by the investigator for this limited participation in the study (unless this situation was adequately described in the original informed consent form [ICF]).

If at any time during the study, the Investigator determines that it is not in the best interest of the subject to continue, the subject will be discontinued from participation. The Investigator can discontinue a subject from study participation at any time if medically necessary or if the subject has failed to follow study procedures or to keep follow-up appointments. Appropriate documentation in the subject's study record and eCRF regarding the reason for discontinuation must be completed. Prior to discontinuing a subject from study participation, the Investigator will discuss his/her intentions with the Medical Monitor or designee.

All subjects who fail to return to the study center for the required follow-up visits will be contacted by phone to determine the reason(s) why the subject failed to return for the necessary visit or elected to discontinue from the study. If a subject is unreachable by telephone after a minimum of 2 documented attempts (1 attempt on 2 different days), a registered letter will be sent requesting that contact be made with the Investigator.

Revance has the right to terminate or to stop the study at any time. Should this be necessary, both Revance and the Investigator will ensure that proper study discontinuation procedures are completed.

7.2. Lost to Follow-up

A subject will be considered lost to follow-up if he or she repeatedly fails to return for scheduled visits and is unable to be contacted by the study center.

Before a subject is deemed lost-to-follow-up, the study center should make every effort to contact the subject (refer to Section 7.1) and reschedule the missed visit as soon as possible. The subject should be counseled on the importance of visit compliance and should be questioned as to whether he or she wishes to continue in the study.

8. STUDY ASSESSMENTS AND PROCEDURES

8.1. Subject Entry Procedures

Subject informed consent must be obtained prior to conducting screening procedures. Each signature must be personally dated by each signatory and the original retained by the PI as part of the study record. A signed copy must be provided to each subject (refer to Section 5.3).

8.2. Schedule of Visits and Procedures

It is recommended that study visits be scheduled at approximately the same time of day throughout the study. The IGA-LCWS and Investigator GAIS should be performed by the same evaluator throughout the study whenever possible. If it is not possible to use the same evaluator throughout the study, two evaluators should examine the subject together and discuss findings for at least 1 prior visit. The SOA is provided in Section 1.3.

8.2.1. Screening Visit

The Screening Visit must take place within 14 days prior to the LCL treatment visit (Day 1 Visit).

The following procedures must be performed and recorded at this visit:

1. Review study procedures and information regarding the study and obtain written informed consent and privacy authorization (as applicable)
2. Review eligibility criteria
3. Obtain medical/surgical history, including prior toxin use, and demographic information, including Fitzpatrick skin phototype
4. Once the investigator has confirmed eligibility, the subject will be enrolled
5. Conduct patient education: Discuss the potential effect of DAXI for injection treatment, explain the PLCWS measurement and the categories of the severity assessment scales, and instruct the subjects to consider depth of lines for LCL severity. Use the provided Patient Education Brochure

■ [REDACTED]

■ [REDACTED]

8. Perform a physical examination. [REDACTED]

■ [REDACTED]

10. Measure and record vital signs (body temperature, respiratory rate, sitting radial pulse, and sitting systolic and diastolic blood pressure); subjects must sit for at 5 minutes prior to having pulse and blood pressure measurements taken

[REDACTED]

12. Collect blood and urine samples for clinical safety laboratory tests (hematology, serum chemistry, PT, and urinalysis)

[REDACTED]

[REDACTED]

[REDACTED]

[REDACTED]

[REDACTED]

[REDACTED]

[REDACTED]

[REDACTED]

The Screening Visit clinical laboratory test results and UPT must be reviewed and signed by the investigator; any abnormal results must be determined to be not clinically significant by the investigator prior to enrollment.

8.2.2. Treatment Visit (Baseline/Day 1)

The LCL treatment visit at Baseline (Day 1 Visit) must be performed within 14 days of the Screening Visit. The LCL dose is administered at this visit. The following procedures must be performed and recorded for each visit:

Prior to Investigational Product Administration

1. Confirm that all screening procedures have been completed, results reviewed, and recorded
2. Review eligibility criteria
3. Update medical/surgical history

[REDACTED]

[REDACTED]

[REDACTED]

[REDACTED]

7. Conduct patient education: Discuss the potential effect of DAXI for injection treatment, explain the PLCWS measurement and the categories of the severity assessment scales, and instruct the subjects to consider depth of lines for LCL severity. Use the provided Patient Education Brochure

[REDACTED]

[REDACTED]

[REDACTED]

[REDACTED]

[REDACTED]

[REDACTED]

11. Physical examination [REDACTED]

[REDACTED]

13. Measure and record vital signs (body temperature, respiratory rate, sitting radial pulse, and sitting systolic and diastolic blood pressure); subjects must sit for 5 minutes prior to having pulse and blood pressure measurements taken

[REDACTED]

16. Update concomitant therapy/medications since the Screening documenting the dose and dosing regimen of all prescription and non-prescription therapies and medications, including herbs, vitamins, or other nutritional supplements (Section 6.3).

Investigational Product Preparation

The assigned investigational product will be prepared by the trained dose preparer according to trial-specific instructions. The prepared investigational product will be provided in a syringe to the investigator for administration.

Investigational Product Administration

Investigational product will be administered by the investigator to injection site in the designated treatment area (Refer to Appendix 2) while the subject is in a seated position.

- 1. Wear protective gloves for investigational product administration.
- 2. Pull subject's hair away from the treatment area.
- 3. Wipe all injection sites with alcohol.

[REDACTED]

8.2.4. Follow-up Visits

At Weeks 2, 4, 8, 12, 16, 20, 24, 28, and 32, the following procedures must be performed and recorded:

- [REDACTED]
- [REDACTED]
- 3. Conduct patient education: discuss the potential effect of DAXI for injection treatment, explain the PLCWS measurement and the categories of the severity assessment scales, and instruct the subjects to consider depth of lines for severity of their LCL. Use the provided Patient Education Brochure

- [REDACTED]

- [REDACTED]
- [REDACTED]
- [REDACTED]
- [REDACTED]

- 13. Collect blood and urine samples for clinical safety laboratory tests (hematology, serum chemistry, and urinalysis) (Week 4 Visit only)

- [REDACTED]

- 17. Assess any new or ongoing AEs since the last visit

- [REDACTED]
- [REDACTED]
- [REDACTED]

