4.4. Visit Schedule

A Screening Visit will be conducted up to 2 weeks prior to enrollment, and subjects will receive investigational product at baseline (Day 1). Following treatment, subjects will complete a paper diary for 2 weeks to capture their assessment of improvement in the appearance of LCL. A follow-up safety phone call will be conducted at Week 1. Post-treatment on-site follow-up visits

will occur at Weeks 2, 4, 8, 12, 16, 20, 24, 28, 32, and 36. The total study duration will be up to 38 weeks, including up to a 2-week screening period. Subjects will be followed for a minimum of 24 weeks post-treatment and up to 36 weeks or until scores return to baseline for the maximal expression IGA-LCWS and PLCWS or until the Week 36 Visit, whichever occurs first. Subjects will then have a Final Evaluation Visit.

Subjects will be evaluated for LCL severity using the Revance-validated 4-point IGA-LCWS and PLCWS at rest and at maximum smile effort.

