8.2.5. Final Evaluation Visit (Week 36) or Early Discontinuation

The following procedures must be performed and recorded at the Final Evaluation Visit for each subject. Following treatment, subjects will be followed for at a minimum of 24 weeks from LCL treatment and up to 36 weeks for safety or until maximal expression scores on the IGA-LCWS and PLCWS return to baseline or Week 36, whichever occurs first. Subjects will then have a Final Evaluation Visit at which time the following procedures must be performed and recorded:

- [REDACTED]
- 2. Conduct patient education: Discuss the potential effect of DAXI for injection treatment, explain the PLCWS measurement and the categories of the severity assessment scales, and instruct the subjects to consider depth of lines for severity of their LCL. Use the provided Patient Education Brochure
- [REDACTED]
- 10. Perform a physical examination [REDACTED]
- [REDACTED]
- 12. Measure and record vital signs (body temperature, respiratory rate, sitting radial pulse, and sitting systolic and diastolic blood pressure)
- [REDACTED]
- 14. Collect blood and urine samples for clinical safety laboratory tests (hematology, serum chemistry, and urinalysis)
- [REDACTED]

If there are no safety concerns, the subject's participation in the study is complete at this visit.

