8.5.2. Assessment and Reporting Requirements

The investigator will assess each subject post-treatment and at each subsequent study visit for the occurrence of AEs. In order to avoid bias in eliciting AEs, subjects should be asked the following non-leading question: “How have you felt since your last visit?” All AEs (serious and non-serious) will be collected from the signing of the ICF until the Final Evaluation Visit. Any AE reported by the subject must be recorded on the source documents and eCRFs.

All AEs will be collected from Day 1 until Week 36 or the Final Evaluation Visit at all timepoints as specified in the SOA (Section 1.3). Medical occurrences that begin before the start of study intervention but after obtaining informed consent will be recorded as well.

All SAEs will be recorded and reported to Revance or designee immediately within 24 hours of their awareness of the event. All fatal or life-threatening SAEs should be telephoned to Revance or the designee’s authorized representative as soon as the investigator learns of the event.

[figure not shown]

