6.5.3.2 Time to Return to, or Time to Loss of, a Given State

The time to return to a given state, or time to loss of a given criterion, will be summarized with point estimates of median duration and 2-sided, 95% CIs, using the log-log transformation by summary cohort. Estimates of survival rates and the 2-sided, 95% CI, using the log-log transformation will also be provided. Kaplan-Meier survival curves will be plotted such that each summary group is a separate line in the same plot. This approach corresponds to the following exploratory endpoints:

- Median time to return to baseline or worse in LCL severity on both the IGA-LCWS and PLCWS at maximum smile

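### Staff must discuss the drug's potential effect together with the self-rating scale at all 10 on-site post-treatment visits, which risks expectation bias in the visit-based subject ratings

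*Protocol*

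**What the plan says.** Protocol 8.2.4 opens its procedure list with "At Weeks 2, 4, 8, 12, 16, 20, 24, 28, and 32, the following procedures must be performed and recorded". Step 3 of that list reads "Conduct patient education: discuss the potential effect of DAXI for injection treatment, explain the PLCWS measurement". It goes on to the severity categories, tells staff to "instruct the subjects to consider depth of lines for severity of their LCL", and refers them to a Patient Education Brochure. Protocol 8.2.5, step 2, has the same instruction for the Final Evaluation Visit (Week 36 or early discontinuation): "Conduct patient education: Discuss the potential effect of DAXI for injection treatment, explain the PLCWS measurement". Sections 8.2.1 and 8.2.2 require it at Screening and, before injection, on Day 1.

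The Disclosure Statement in the Protocol synopsis says that nobody is blinded and that every subject receives DAXI. SAP 3.1.2 adds that the study is not randomized.

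For adverse events, Protocol 8.5.2 takes care over wording: "In order to avoid bias in eliciting AEs, subjects should be asked the following non-leading question".

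The subject's own score enters several results. Protocol 9.4.1 summarizes subject-assessed responder and time-to-event endpoints in the same way as the investigator's. SAP 6.5.3.2 lists as an exploratory endpoint "Median time to return to baseline or worse in LCL severity on both the IGA-LCWS and PLCWS at maximum smile". Protocol 4.4 and 8.2.5 use the same pair of scales to decide when follow-up ends, after a minimum of 24 weeks.

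**The concern.** The education step does two jobs. One is neutral: it explains the scale and directs attention to line depth. The other raises what the drug may do. Before injection the second job informs the subject. After injection it comes alongside the subject's rating of the result, from someone who knows the treatment, in a trial with no untreated arm to show how much of a rating is expectation.

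At stake are the absolute subject-assessed response rates and satisfaction results in each cohort, and the duration result wherever PLCWS decides it. If expectation shifts these ratings, the data cannot separate the shift from drug effect. The adverse-event question shows that the protocol recognises leading prompts as a source of bias. No comparable limit on what staff say is visible for the subject's efficacy ratings.

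**Working it through.** The plan states no figure for this point, so there is none to reproduce. The check is a visit count, a comparison of timing with each outcome, and two short calculations.

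**1. Visits carrying the instruction**
- Protocol 8.2.4: Weeks 2, 4, 8, 12, 16, 20, 24, 28 and 32 = 9 visits.
- Protocol 8.2.5: Week 36 or Final Evaluation = 1 visit.
- Total: 9 + 1 = 10 of 10 scheduled on-site post-treatment visits. With Screening and Day 1, it is 12 of 12 on-site visits.
- A subject whose follow-up ends at Week 24 has 7 (Weeks 2, 4, 8, 12, 16, 20 and 24).
- The remaining contact is not a visit: "A follow-up safety phone call will be conducted at Week 1".

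**2. Which outcomes are exposed**
- *Exposed:* PLCWS, subject GAIS, FASE, FACE-Q and satisfaction, all rated by the subject at post-treatment visits (Protocol 8.3.2 to 8.3.5 and 8.3.6.1.2).
- *Exposed in part:* the joint return-to-baseline endpoint and the end-of-follow-up rule, through PLCWS.
- *Not directly exposed:* the primary endpoint, which the investigator rates on the IGA-LCWS at Week 4 (SAP 2.2.1).
- *Not directly exposed:* diary onset (SAP 6.5.3.3). The diary covers the 2 weeks after treatment (Protocol 4.4), so it essentially precedes the first post-treatment education at Week 2. Only the Screening and Day 1 education comes before it.

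**3. Scale of a shift in a response rate**
- Input: about 16 subjects per cohort (Protocol 4.1).
- Change per subject who crosses the responder threshold = 1/16 = 6.25 percentage points.
- If 1 to 3 subjects crossed (an assumption, for illustration): 1/16 to 3/16 = 6.25 to 18.75 points.
- A shift that does not cross the threshold changes nothing. Scoring 2 instead of 3 leaves a 0-or-1 response rate where it was.

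**4. Scale of a shift in duration**
- Let *a* be the week when IGA-LCWS returns to baseline and *p* the week when PLCWS does. Assume that each stays there once returned. The joint time is max(*a*, *p*).
- From Week 4 on, visits are 4 weeks apart, so a one-visit delay in PLCWS changes the joint time by max(*a*, *p* + 4) − max(*a*, *p*).
- PLCWS last: *a* = 20, *p* = 24 gives 28 − 24 = 4 weeks.
- IGA-LCWS last: *a* = 24, *p* = 20 gives 24 − 24 = 0 weeks.
- So a delay adds 4 weeks only when PLCWS is the last scale to return, or returns at the same visit as the IGA-LCWS.
- The end of follow-up moves only if the joint time then passes Week 24. With *a* = 16 and *p* = 20, the joint time moves from 20 to 24, but follow-up ends at Week 24 either way.

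**The case against.** Much of the case on the other side stands, and it limits the point.

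- **Order.** Most steps in both lists are redacted, and no rating step is visible in either. That education comes before rating is inferred from its low step number (3, and 2 at the final visit) and from the purpose of explaining a scale. The inference is reasonable but not shown.
- **Direction.** A reader might infer that subjects are coached to report benefit. The documents do not support that. The text speaks only of a potential effect, and the brochure is not among the documents. The discussion could cover unwanted effects or wearing off, and Protocol Section 2 describes toxin effect as time-limited. A reminder that the effect fades could move late ratings toward baseline and shorten duration.
- **Scope.** A reader might also infer that every subject-reported endpoint, or the primary endpoint, is primed. Diary onset and the investigator-rated primary endpoint fall outside, as shown above.
- **Safeguards.** It would be unfair to say that the protocol does for efficacy the reverse of what it does for adverse events. Subjects receive the forms directly and use a mirror, they rate before the investigator's IGA-LCWS, and subject GAIS is compared with a baseline photograph (Protocol 8.3.2 and 8.3.3). These help, but none limits what staff say about drug effect, and no photograph is described for PLCWS.
- **Dose comparison.** The wording is the same for all cohorts, so by itself it favours no dose. Uniform wording still leaves each cohort's absolute rates and durations exposed, and these are what the SAP reports.
- **Weight.** No formal tests are planned (Protocol 9.4), and the duration endpoint is exploratory. Subjects already know their treatment, so removing the clause does not remove open-label expectation.

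**Conclusion.** The point holds as an avoidable risk of modest weight. An instruction to discuss drug effect is tied to the self-rating scale at all 10 on-site post-treatment visits, in a design that cannot separate expectation from drug effect. It bears on five visit-based subject-reported outcomes. It also bears on the joint duration endpoint and the end of follow-up, but only when PLCWS is the last scale to return.

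No size or direction of bias can be derived from the documents. The 6.25 points per subject and the 4 weeks per delayed visit show how sensitive small cohorts and a four-weekly grid are; they are not estimates. They assume that a shift crosses a responder threshold, or that PLCWS sets the joint return time. The conclusion also assumes that education comes before the subject's ratings, which the visible text suggests but does not prove.

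**What to change.** In Protocol 8.2.4, step 3, and 8.2.5, step 2, delete the clause about discussing the potential effect of DAXI. Limit education at these visits to neutral scale instruction: the PLCWS categories and attention to line depth. Alternatively, state that any discussion of effect takes place only after all subject ratings for that visit are complete. Deletion is cleaner, because a discussion held after one visit's ratings still comes before the next visit's. Leave the discussion at Screening and before treatment on Day 1 as it is.

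The cost is one clause in two visit lists and a line in site training. If the brochure mixes effect and scale content, a short scale-only sheet would be needed for post-treatment use. No visit, rating or safety step is lost; adverse events have their own step in 8.2.4 (step 17).
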